1. SUMMARY

Rationale

The worldwide practice of fluid and vasopressor therapy in critically ill invasively ventilated patients is uncertain. Indeed, it is unclear whether there is a difference in fluid and vasopressor therapy in these patients between Low- and Middle-income Countries (LMICs) and High-income Countries (HICs).

Objective

To determine various aspects of fluid and vasopressor therapy in critically ill invasively ventilated patients in LMICs and HICs.

Hypothesis

There is substantial worldwide variation in practice of fluid and vasopressor therapy in critically ill invasively ventilated patients.

Study design

International, multicenter, observational study in critically ill invasively ventilated patients; data are captured during a predefined period per geographic region or country.

Study population

Critically ill invasively ventilated patients.

Main study parameter/endpoint

The primary outcome is a composite of various aspects of fluid therapy, including total volumes of types of fluids administered in the first three days after start of invasive ventilation and total volume of fluids infused in the first seven days after start of invasive ventilation. Secondary outcomes include timing of start, type, and duration of continuous administration of vasopressors; timing of start, infusion time and types of administered diuretics; daily urine output and cumulative fluid balances; and typical ICU outcomes, like duration of ventilation, lengths of stay in ICU and hospital, and mortality in the ICU and hospital, and at day-28, -60 and -90.

Nature and extent of the burden and risks associated with participation, benefit and group relatedness

Because of the observational design of the study using routinely collected data, there is no additional burden for the patient. Collection of data from ICU charts or electronic medical records systems is of no risk to the patients.

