6.1.2. Secondary study parameters

- Time of start of vasopressors;
- Route of administration for vasopressors (i.e. central vs. peripheral route);
- Types of vasopressor used;
- Daily urine output;
- Cumulative fluid balance;
- Timing of start, type and infusion time (i.e. bolus vs. continuous infusion) of administered diuretic;
- Incidence of atrial arrhythmias;
- Incidence of acute respiratory distress syndrome (ARDS)
- Incidence of renal replacement therapy;
- Incidence of persistent renal dysfunction, defined as the need for renal replacement therapy at ICU discharge;
- ICU length of stay, defined as the time between ICU admission and discharge or death;
- Hospital length of stay, defined as the time between hospital admission and discharge or death;
- Duration of ventilation, defined as the time between initiation of invasive ventilation and successful liberation of ventilation.
- Ventilator-free days and alive at day 28, defined as 28 - x if successfully liberated from ventilation x days after initiation. If subject dies within 28 days ventilator-free days is set to 0;
- All-cause ICU mortality, defined as any death during ICU stay;
- All-cause in-hospital mortality at day 28, defined as any death during hospital stay before or on study day 28;
- All-cause in-hospital mortality at day 60, defined as any death during hospital stay before or on study day 60;
- All-cause in-hospital mortality at day 90, defined as any death during hospital stay before or on study day 90;

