6.2.3. Data to be collected

The following data will be collected for all enrolled patients admitted to ICU during the screening period. Day 0 is defined as the day of initiation of invasive ventilation. Day 1 is defined as the first full calendar day after initiation of invasive ventilation. In patients that are not invasively ventilated at ICU admission day -3 to -1 are defined as the days before intubation but after ICU admission.

A. At ICU admission;

- Gender, male/female/other;
- Age, years;
- Weight, kg;
- Length, cm;
- Ethnicity, Black, East Asian, Indigenous (First Nations, Inuk/Inuit, Métis), Latin American, Middle Eastern, South Asian, Southeast Asian, White;
- Reason for ICU admission;
- Traumatic brain injury?;
- Sub-arachnoid hemorrhage?
- Date of ICU admission;
- Date of start of invasive ventilation;
- Did the patient receive non-invasive ventilation or high-flow nasal oxygen prior to intubation, if so: on which day?;
- Serum creatinine, $\mu\text{mol/L}$ or mg/dL , lowest in the last year, if available; and
- If the reason for ICU admission was burns: what was the cause of the burn and how much total body surface area is affected by the burns
- If the reason for ICU admission was sepsis, what was the focus of the sepsis (e.g. respiratory, abdominal)

B. On day 0;

- Type and volume, ml, of each fluid infusion (including medication and parenteral nutrition);
- Type and volume of oral fluids;
- Anuria ≥ 12 hours?, yes/no;
- Urine output, ml, over 24 hours;
- Extracorporeal life support, venoarterial/venovenous/no;

- Renal replacement therapy, yes/no, if yes;
 - Volume extracted by ultrafiltration, ml, over 24 hours;
- Cumulative fluid balance, ml;
- Loop diuretics given, yes/no, if yes;
 - Furosemide, yes/no, if yes;
 - (if no furosemide used) Bumetanide, yes/no, if yes;
 - (if no bumetanide or furosemide used) Torasemide, yes/no, if yes;
 - (if no Torasemide, bumetanide, furosemide used) Edecrin, yes/no;
- Additional diuretic given (thiazide, carbonic anhydrase inhibitor or mineralocorticoid antagonist), yes/no;
- Serum creatinine, $\mu\text{mol/L}$ or mg/dL , at a convenient fixed time point;
- Serum hemoglobin, $\mu\text{mol/L}$ or mg/dL , at a convenient fixed time point;
- Serum albumin, at a convenient fixed time point;
- Vasopressors initiated, yes/no, if yes;
 - Time between ICU admission and initiation of vasopressors, hours;
 - Drug(s) used as vasopressor;
- Mean arterial pressure (MAP) mmHg, at a convenient fixed time point;

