- Heart rate, beats/min, at a convenient fixed time point;
- Atrial fibrillation or flutter during the last day, yes/no;
- Arterial or venous lactate, if measured, mmol/L , highest and lowest value;
- (Central) venous oxygen saturation ($S(c)VO_2$), mmol/L , if measured, highest and lowest value;
- Arterial partial pressure of oxygen (PaO_2), kPa or mmHg , at a convenient fixed time point;
 - (if no PaO_2 is known) Peripheral arterial oxygen saturation (SpO_2), percentage, at a convenient fixed time point;
- Inspired oxygen fraction, %, at time of PaO_2 or (if no PaO_2 is known) SpO_2 ;
- Suspected or confirmed infection that causes organ dysfunction (sepsis) yes/no;
- Was there new-onset (<7 days) respiratory symptoms, or acute worsening of respiratory symptoms?, yes/no, if yes;
- Are there bilateral opacities on chest imaging (including lung ultrasound), yes/no;
- If there was hypoxemia, was the hypoxemia explained by cardiac failure, yes/no?

- Richmond Agitation Sedation Scale (RASS), highest value of this day after intubation; and
- Sequential Organ Failure Assessment (SOFA) score.

C. Daily on day 1 and day 2;

- Type, volume, ml, and rate, ml/min, of each separate fluid infusion (including medication and parenteral nutrition);
- Type and volume of oral fluids;
- Anuria \geq 12 hours?, yes/no;
- Urine output, ml, over 24 hours;
- Extracorporeal life support, venoarterial/venovenous/no;
- Renal replacement therapy, yes/no, if yes;
 - Volume extracted by ultrafiltration, ml, over 24 hours;
- Cumulative fluid balance, ml;
- Loop diuretics given, yes/no, if yes;
 - Furosemide, yes/no, if no;
 - (if no furosemide used) Bumetanide, yes/no, if no;
 - (if no bumetanide or furosemide used) Torasemide, yes/no;
 - (if no Torasemide, bumetanide, furosemide used) Edecrin, yes/no;
 - Additional diuretic given (thiazide, carbonic anhydrase inhibitor or mineralocorticoid antagonist), yes/no;
- Serum creatinine, $\mu\text{mol/L}$ or mg/dL , at a convenient fixed time point;
- Serum hemoglobin, $\mu\text{mol/L}$ or mg/dL , at a convenient fixed time point;
- Serum albumin, at a convenient fixed time point;
- Vasopressors given, yes/no, if yes;
 - Time between ICU admission and initiation of vasopressors, only if not initiated on day 0, hours;
 - Drug(s) used as vasopressor;
- MAP, mmHg, at a convenient fixed time point;
- Heart rate, beats/min, at a convenient fixed time point;
- Atrial fibrillation or flutter during the last day, yes/no;

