- Arterial or venous lactate, mmol/L , at a convenient fixed time point;
- Serum sodium, mmol/l , at a convenient fixed time point;

- Serum chloride, mmol/l, at a convenient fixed time point;
-
- S(c)VO₂, mmol/L, highest and lowest value;
- PaO₂, kPa or mmHg, at a convenient fixed time point;
- (if no PaO₂ is known) Peripheral arterial oxygen saturation (SpO₂), percentage, at a convenient fixed time point;
- Inspired oxygen fraction, %, at time of PaO₂ or (if no PaO₂ is known) SpO₂;
- Was there new-onset (<7 days) respiratory symptoms, or acute worsening of respiratory symptoms?, yes/no, if yes;
- Are there bilateral opacities on chest imaging (including lung ultrasound), yes/no;
- If there was hypoxemia, was the hypoxemia explained by cardiac failure, yes/no?
- Richmond Agitation Sedation Scale (RASS), highest value of the day; and
- SOFA score.

D. Daily on day 3 to 7 or ICU discharge; and on day -1, day -2 and day -3;

- Total volume of infused fluid, ml, over 24 hours
- Cumulative fluid balance, ml, over 24 hours;
- Urine output, ml, over 24 hours;
- Extracorporeal life support, venoarterial/venovenous/no;
- Renal replacement therapy, yes/no, if yes;
 - Volume extracted by ultrafiltration, ml, over 24 hours;
- Loop diuretics given, yes/no, if yes;
 - Furosemide, yes/no, if no;
 - (if no furosemide used) Bumetanide, yes/no, if no;
 - (if no bumetanide or furosemide used) Torasemide, yes/no;
 - (if no Torasemide, bumetanide, furosemide used) Edecrin, yes/no;
 - Additional diuretic given (thiazide, carbonic anhydrase inhibitor or mineralocorticoid antagonist), yes/no;
- Serum creatinine, µmol/L or mg/dL, at a convenient fixed time point;
- Serum hemoglobin, µmol/L or mg/dL, at a convenient fixed time point;
- Serum albumin, at a convenient fixed time point;
- Vasopressors used, yes/no, if yes;
 - Drug(s) used as vasopressor;

- MAP, mmHg, at a convenient fixed time point;
- Heart rate, beats/min, at a convenient fixed time point
- Atrial fibrillation or flutter during the last day, yes/no;
- Arterial or venous lactate, mmol/L, at a convenient fixed time point;
- Serum sodium, mmol/l, at a convenient fixed time point;
- Serum chloride, mmol/l, at a convenient fixed time point;
- PaO₂, kPa or mmHg, at a convenient fixed time point;
- (if no PaO₂ is known)) Peripheral arterial oxygen saturation (SpO₂), percentage, at a convenient fixed time point;
- Inspired oxygen fraction, %, at time of PaO₂ or (if no PaO₂ is known) SpO₂; and
- SOFA score.

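### The diuretic endpoint includes bolus versus continuous infusion, but the data list has no field for it on any day; the branching of the diuretic items also needs repair

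*Protocol*

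**What the plan says.** The secondary parameter in Protocol Section 6.1.2 has three parts: "Timing of start, type and infusion time (i.e. bolus vs. continuous infusion) of administered diuretic". The Summary names the same three: "timing of start, infusion time and types of administered diuretics".

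Section 6.2.3 presents its lists as the study's data set: "The following data will be collected for all enrolled patients admitted to ICU during the screening period". Diuretics appear in three of them: list B (day 0), list C (days 1 and 2) and list D (days 3 to 7, and days -3 to -1). Lists A, E and F, for admission, events and follow-up, have no diuretic item.

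Each of the three lists opens with a yes/no on loop diuretics and then works through the agents in a fixed order. On day 0 the second step reads "if no furosemide used) Bumetanide, yes/no, if yes"; in lists C and D it reads "if no furosemide used) Bumetanide, yes/no, if no". The third step is "if no bumetanide or furosemide used) Torasemide, yes/no", and Edecrin is asked about only when none of the first three was used. Each list also contains "Additional diuretic given (thiazide, carbonic anhydrase inhibitor or mineralocorticoid antagonist), yes/no". On day 0 this stands as an item of its own. In lists C and D it is indented below the loop-diuretic question.

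**The concern.** An endpoint can be reported only if its components are recorded. Two of the three components, start and type, have at least some fields behind them. The third, mode of infusion, seems to have none. The study sets out to describe practice, so a component that is named but not collected is simply lost: sites would follow the list faithfully and the result table would have an empty row. An analysis plan written later, as Section 8.2 foresees, cannot repair this.

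The branching raises a further question about the type component. If one agent is asked about only when another was not given, combinations disappear. If non-loop drugs are asked about only when a loop diuretic was given, their use alone disappears as well.

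**Working it through.** No power, error-rate or sample-size figure enters this point, so the plan has no number to reproduce. The check maps each endpoint component to the fields in Section 6.2.3.

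**Step 1: infusion mode.**

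| Days | List | Diuretic mode field | Infusion detail collected | Can mode be inferred? |
|---|---|---|---|---|
| -3 to -1 (3 days) | D | none | total daily volume | no |
| 0 (1 day) | B | none | "Type and volume, ml, of each fluid infusion (including medication and parenteral nutrition"; no rate | not from type and volume alone |
| 1 and 2 (2 days) | C | none | type, volume and rate per infusion, medication included | only if the drug is identified |
| 3 to 7 (5 days) | D | none | total daily volume | no |

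Possible days: 3 + 1 + 2 + 5 = 11. Days with a dedicated field: 0 of 11. Days with a conceivable proxy: 2 of 11, which leaves 11 - 2 = 9 without one. A patient already ventilated at ICU admission has no negative days, so the proxy covers at most 2 of 1 + 2 + 5 = 8 days.

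**Step 2: loop agents.** The recording order is furosemide, bumetanide, torasemide, Edecrin, and the chain is asked afresh each day.

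- One agent per day, changed overnight: both agents are recorded, each on its own day.
- Furosemide and bumetanide on the same day: furosemide only is recorded.
- Furosemide changed to bumetanide during day 2, bumetanide continued: bumetanide first appears on day 3.

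The loss is therefore confined to a second loop agent on the same calendar day, and it always favours the earlier-listed drug. By contrast, the vasopressor item in the same lists allows several drugs to be entered. The day-0 version is also worded inconsistently: its steps end with an instruction for a positive answer, but what follows is the next step of the chain, which applies only after a negative one.

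**Step 3: additional diuretic, in a patient given a non-loop diuretic and no loop diuretic.**

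- Day 0: the item is reachable, so use is recorded.
- Days 1 to 7 and -3 to -1: if the indentation reflects the form's logic, the item is never reached and use is not recorded.

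On that reading, a patient ventilated from admission would show use on day 0 and then none. A patient intubated later would show an isolated day-0 peak, because list D also governs the days before intubation.

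**Step 4: what remains obtainable.** Any loop-diuretic use by day, and the first calendar day of such use within the observed window, can be derived on every reading.

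**The case against.** The strongest reply has four parts.

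*The list is not the eCRF.* The electronic form may contain a mode item. It may, but the Protocol presents the list as what is collected, and the endpoint and the list then disagree within one document. This part does not remove the point.

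*Mode might be inferred from rate on days 1 and 2.* This stands in part. A reader might conclude that no patient at all could be evaluated for bolus versus continuous use. The documents do not support that, because list C records the rate of each infusion with medication included. What they support is that there is no dedicated field, and an uncertain proxy on two days.

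*The chain does little harm.* This largely stands. A reader might infer that every agent other than furosemide is under-counted. That is too broad: changes between days are kept, any-loop use is kept, and the chain does not touch non-loop drugs. The Protocol says nothing about how often two loop agents are given on one day.

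*The nesting rests on indentation in text read from a PDF.* This stands as a caution. Indentation does not follow logic consistently in these lists: the oxygen-saturation fallback is indented on day 0 but not in lists C and D, and the chest-imaging question follows a conditional without being indented. On the other side, lists C and D agree with each other and differ from B. The item could also be meant as an add-on to a loop diuretic, in which case the fault is inconsistency with day 0. A reader might take the loss of non-loop-only use as established; it is possible, not shown.

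**Conclusion.** The point holds for infusion mode. It is a named part of a secondary endpoint, stated in two places, with a dedicated field on 0 of 11 possible days and at best a conditional proxy on 2. This rests on the wording of the lists alone and needs no assumption about frequency.

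The same-day loss of a second loop agent is also explicit in lists B, C and D, but is a lesser matter of unknown size. The nesting of the additional-diuretic item is to be confirmed on the original layout or the eCRF before anything is concluded from it. No percentage can be attached to either: the documents give no rate of combined loop use or of non-loop use alone, so any figure would only restate an assumption.

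The stakes are those of one descriptive secondary item. The primary parameter, the mortality outcomes and the sample-size reasoning are unaffected.

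**What to change.** Use one identical diuretic block on day 0, days 1 and 2, days 3 to 7 and days -3 to -1:

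- each loop agent as an independent yes/no, without the exclusion chain;
- the additional-diuretic item at the top level, not conditional on loop-diuretic use;
- one item for mode: bolus, continuous or both.

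If mode is not going to be collected, remove infusion time from Section 6.1.2 and from the Summary together; removing it from only one leaves the two in conflict. In either case, check the position of the additional-diuretic item against the original layout and the eCRF.

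The cost is a change to the form's branching and a small amount of entry work, about one more tick per diuretic day. Narrowing the endpoint adds no entry work but gives up the mode comparison.

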6.2.4. Follow-up

Participants are subject to follow-up until hospital discharge, day 90 or death.

7. SAFETY REPORTING

7.1. Adverse and serious adverse events

Not applicable

7.2. Follow-up of adverse events

Not applicable

7.3. Data Safety Management Board (DSMB)

Not applicable

8. STATISTICAL ANALYSIS

8.1. Descriptive statistics

Data are expressed as means (standard deviation), medians (interquartile range) and proportions as appropriate. Mann–Whitney U–tests are used to compare continuous variables and Fisher’s exact tests are used for categorical variables. Comparisons between and within groups are performed using one–way ANOVA with post–hoc analyses for continuous variables.

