3. AIMS AND HYPOTHESES

3.1. Aims

To determine the current practice of fluid and vasopressor therapy in critically ill invasively ventilated patients (primary); to compare fluid and vasopressor therapy between Low- and Middle-income Countries (LMICs) and High-income Countries (HICs) and to determine the associations of various aspects of fluid and vasopressor therapy with clinical outcomes.

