4. STUDY DESIGN

Prospective, international, multicenter, observational study in critically ill invasively ventilated patients during a 28–day period in a convenience sample of hospitals globally.

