5. STUDY POPULATION

5.1. Population (base)

We will collect data in critically ill invasively ventilated patients that receive ventilation for at least 24 hours. We expect a minimum of 200 ICUs from 30 countries to participate in this prospective international multicenter observational study. Patients will be screened daily during a 28–day period. A registry of limited demographic data will be compiled on all screened patients. Data regarding fluid administration, vasopressor use, diuretics use, oxygen exchange, and kidney function will be collected daily from the start of invasive ventilation. Collection will be retrospective, for the previous day. Clinical complications will be evaluated on day 90 day after start of invasive ventilation, death or hospital discharge, whichever comes first.

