5.5. Sample size calculation

No formal sample size calculation is necessary for the primary endpoint. However, for investigating associations of aspects of fluid and vasopressor therapy with mortality using logistic regression and adjusting for a limited set of pre-specified confounders, we estimate to need 150 ‘events’ using the 10 event per variable rule of thumb. As fluid and vasopressor management is particularly important in patients with acute respiratory distress (ARDS), we will need at least 150 events in this subgroup. With an incidence of ARDS of approximately 20% and a mortality rate of 30%, we estimate to need 2500 patients to have 150 events in patients with ARDS (37). Assuming that a participating ICU has 50 unique admissions in 4 weeks on average, of which 25% is invasively ventilated for > 24 hours, we expect to need a minimum of 200 participating ICUs (38-40).

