8.2. Plan of analysis

Subjects that are transferred to another ICU in the first three calendar days of ICU admission will be excluded from analysis. Subjects that are transferred to another ICU after the first three calendar days, but before seven days are excluded from analysis of the secondary endpoints. Patients admitted due to pancreatitis, burns, diabetic ketoacidosis, severe rhabdomyolysis and sub-arachnoid bleeding will be analyzed separately and excluded from analysis if less than 30 subjects are included in each category. Subjects diagnosed with sepsis or ARDS during the first three calendar days of ICU admission will be part of a subgroup analysis. Associations with outcomes will be assessed through regression modelling. Time to event variables are analyzed using Cox regression and visualized by Kaplan–Meier plots. For each analysis proposed, a complete statistical analysis plan will be prepared, finalized and made available before starting the analyses. Statistical analyses are conducted using R (www.r-project.org). A *P*–value of less than 0.05 is considered statistically significant.

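### The tests named in section 8.1 assume independent patients, but an LMIC-versus-HIC comparison is clustered by ICU and country, so its p-values will be too small by an amount that depends on an unstated ICC

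*Protocol*

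**What the plan says.** Section 3.1 of the protocol lists, after a descriptive primary aim, the aim "to compare fluid and vasopressor therapy between Low- and Middle-income Countries (LMICs) and High-income Countries (HICs"). Section 3.2 turns this into a hypothesis that the two groups differ. It is the only between-group comparison that the aims name.

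Section 8.1 gives the tests: "Mann–Whitney U–tests are used to compare continuous variables and Fisher’s exact tests are used for categorical variables", and "Comparisons between and within groups are performed using one–way ANOVA with post–hoc analyses for continuous variables". Section 8.2 sets the threshold: a P "value of less than 0.05 is considered statistically significant". Section 8.2 also mentions regression for associations with outcomes and Cox models for times to event, and promises a full SAP before each analysis. It assigns no other test to the comparison of practice between income groups.

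On structure, section 4 describes recruitment "in a convenience sample of hospitals globally", and section 5.1 states: "We expect a minimum of 200 ICUs from 30 countries to participate". The protocol nowhere mentions clustering, random effects, GEE, robust variance or an ICC.

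**The concern.** Mann–Whitney, Fisher's exact and one-way ANOVA take each patient as an independent observation. Here patients share an ICU and a country, and the grouping factor is a property of the country. Every patient in an ICU or country therefore falls on the same side of the comparison, so none of the shared local habit cancels out and the variance of the contrast carries the full design effect.

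The protocol itself expects local habit to matter. Section 2.4 describes marked differences between countries in the fluids prescribed, and section 2.5 says clinicians disagree within and between countries. At stake is the second hypothesis: a difference between LMICs and HICs could be declared significant because a few countries or large centres happen to have distinctive practice, and not because income group matters.

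**Working it through.** **The plan's own figures.** Section 5.5 says "With an incidence of ARDS of approximately 20% and a mortality rate of 30%, we estimate to need 2500 patients to have 150 events". Those events are deaths within the ARDS subgroup, so the sum is 150 / (0.20 × 0.30) = 2500. For centres it starts from: "Assuming that a participating ICU has 50 unique admissions in 4 weeks on average, of which 25% is invasively ventilated for > 24 hours". That gives 50 × 0.25 = 12.5 patients per ICU, and 2500 / 12.5 = 200 ICUs. Both figures reproduce exactly. They rest on an events-per-variable rule for a mortality model, not on the income-group comparison.

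**Cluster sizes.** Per ICU, m = 2500 / 200 = 12.5. Per country, c = 2500 / 30 = 83.3.

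**Formulas**, with equal cluster sizes and a grouping factor constant within clusters:

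- ICU clustering only: DE = 1 + (m − 1) × ICC
- Country clustering only: DE = 1 + (c − 1) × ICC
- Both: DE = 1 + (m − 1) × (ρ_ICU + ρ_country) + (c − m) × ρ_country
- True type I error = 2 × [1 − Φ(1.96 / √DE)]

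The protocol does not state sidedness; two-sided 5% is assumed. Every ICC below is an assumption.

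| Assumed ICC | DE | Effective N = 2500 / DE | True type I error |
|---|---|---|---|
| ICU 0.01 | 1.115 | 2242 | 6.3% |
| ICU 0.02 | 1.230 | 2033 | 7.7% |
| ICU 0.05 | 1.575 | 1587 | 11.8% |
| ICU 0.10 | 2.150 | 1163 | 18.1% |
| ICU 0.20 | 3.300 | 758 | 28.1% |
| Country 0.01 | 1.823 | 1371 | 14.7% |
| Country 0.02 | 2.647 | 945 | 22.8% |
| Country 0.05 | 5.117 | 489 | 38.6% |
| ICU 0.05 + country 0.02 | 3.222 | 776 | 27.5% |

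The last row in full: 1 + 11.5 × 0.07 + 70.83 × 0.02 = 1 + 0.805 + 1.417 = 3.222.

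**Simulation check.** 2000 replicates were run with about 2500 patients, 200 ICUs and 30 countries split 15/15 (an assumption), and no true income effect. The Mann–Whitney test was applied to a skewed outcome and Fisher's test to a binary outcome with 30% prevalence.

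| Assumed ICC | Mann–Whitney rejects | Fisher rejects |
|---|---|---|
| None | 5.8% | 5.1% |
| ICU 0.05 | 11.6% | 7.8% |
| ICU 0.10 | 16.9% | 11.9% |
| ICU 0.20 | 26.7% | 20.9% |
| ICU 0.05 + country 0.02 | 28.1% | 20.4% |

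Without clustering both tests are close to 5%, so the excess comes from clustering. The Mann–Whitney results follow the formula. Fisher's are lower, as expected: the ICC was set on the underlying continuous scale, and cutting it into yes/no weakens the correlation. ANOVA was not simulated.

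**The case against.** **Section 8.1 does not name its groups.** It is headed as descriptive statistics and does not mention income group. This stands as a limit: the link to LMIC versus HIC is an inference. It is a strong one, because no other between-group comparison appears in the aims and no other test is given for this one.

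**The SAPs will deal with it.** Section 8.2 promises them, and model detail properly belongs there. But section 8.1 does not leave the tests open. A SAP that follows it inherits the problem, and one that accounts for clustering has to override it.

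**The size is unknown.** This stands. A reader might infer that the p-values are bound to be grossly too small. The protocol gives no ICC, and at an ICU-only ICC of 0.01 to 0.02 the error rate is only 6% to 8%. The account of geographical variation in section 2.4 supports a country-level ICC above zero, but not any particular value.

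**Stronger readings that the text does not support.**

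- A reader might infer that the primary hypothesis of large variation is left without any estimate. It is not: section 8.1 plans standard deviations, interquartile ranges and proportions, and section 3.2 does not define variation as a between-ICU or between-country variance.
- A reader might take the within-group comparisons to be of repeated daily values. Section 8.1 does not say so.
- A reader might hold that the comparison must be adjusted for case-mix or SOFA. An unadjusted contrast is a legitimate answer to the stated aim, and SOFA is scored on the same days as the treatments being compared, so adjusting for it could remove part of the practice difference.
- A reader might extend the criticism to the outcome regressions. Section 8.2 only names regression and rules nothing out; its form can be left to the SAP.

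**Conclusion.** The point holds in a limited form. The only tests the protocol names for comparing groups ignore a structure that it describes itself, and for a factor fixed at country level the direction of the error is certain: any positive ICC makes the p-values too small. Its size is conditional. A nominal 5% test would reject about 6% to 28% of the time for ICU-only ICCs of 0.01 to 0.20, about 15% to 39% for country-only ICCs of 0.01 to 0.05, and about 28% for ICU 0.05 plus country 0.02 (simulated: about 28% for Mann–Whitney and 20% for Fisher).

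These figures assume 2500 patients, equal cluster sizes, two-sided testing and, in the simulation, an even split of countries. The country component matters most, because even an ICC of 0.01 at that level roughly triples the error rate. The problem is confined to inferential comparisons between income groups, or between regions made up of whole countries. The descriptive results for the primary aim stand.

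**What to change.** Amend section 8.1 so that Mann–Whitney, Fisher's exact and one-way ANOVA are not used for LMIC-versus-HIC or regional comparisons. Replace them with one of the following:

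- mixed models with random intercepts for ICU nested in country, linear on a suitably transformed volume for continuous items and logistic for binary items; or
- GEE or regression with cluster-robust variance, clustered at country level, which also covers ICUs because they are nested in countries.

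Either route needs a small-sample correction, since the contrast rests on about 30 countries. State in section 8.1 that income group is the factor being compared, so that the link to the aim no longer has to be inferred. As an option, report the ICU and country variance components as a supplementary description of practice variation.

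The cost is a wording change and no extra patient assessments. ICU and country identifiers must be attached to each record; the data list in section 6.2.3 does not name them, so confirm that the electronic CRF holds them. The price in results is wider confidence intervals and fewer nominally significant findings.
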